4.2 Discussion of study design

The first part of this study is open label, single dose escalation. The aim is to find a safe dose that is tolerated in the target patient population. Doses will be escalated at intervals between patients, guided by a statistical model and an independent Data Monitoring Committee. The starting and maximum doses (i.e. dose range) to be investigated is based on a Phase 3 study [IMPRES (10)] and clinical experience. Our planned sample size, as is generally the case for Phase I trials, is dictated by practical constraints, even more so when the condition being treated is rare (as is PAH). However, simulation studies of the most likely scenario based on the IMPRES trial (10) and expert opinion have shown that a sample size of 13 resulted in a 90% chance of recommending a dose with an associated toxicity within 10% of the target toxicity level (20%) in the most likely scenario. We will be updating the skeleton graph -see Section 10- and revising the number of patients required overall after each patient is treated. We will also consider criteria for extending the sample size if needed and feasible.

The recruitment rate is dictated by the time to assess safety and tolerability at each dose. The decision to escalate dose, identify the highest tolerated dose, and Go/No-Go decision for Part 2 will be made by the independent Trial Safety and Data Monitoring Committees, comprising of lead clinician(s), and oncologist with expertise in the use of Imatinib and a Senior Trial Statistician.

4.3 Selection of study population

Patients participating in this study are adult males and females with symptomatic PAH as defined by the eligibility criteria below. No deviations will be made to the eligibility criteria.

PAH is a rare condition. Patients with PAH attend one of 8 UK specialist centres in the UK for diagnosis and management decisions. Currently these centres have recruited over 650 patients with well-defined PAH to a cohort study. These patients are in regular follow-up and have been consented to recall to future clinical studies. We anticipate recruiting 1 to 2 patients per month. This is based on a recent academic-led study of tocilizumab in PAH and the expertise of the recruiting centres in clinical studies in PAH.

The Covid-19 pandemic has changed clinical practice, with many more consultations taking place by telephone or video conferencing. This is facilitated by the use of remote monitoring − See Figure 5. The PAH cohort has an expanding number of patients with an implanted CardioMEMS[™] Heart Failure system and a Fitbit activity monitor as part of the FIT-PH study (Feasibility of Novel Clinical Trial Infrastructure, Design and Technology for Early Phase Studies in Patients with Pulmonary Hypertension; Ethics approval 19/YH/0354). These have been under follow-up for a mean of 7 months and are stable.

This patient group provide daily data about their health (level of physical activity, day and night cardiac rate and rhythm, heart rate variability, thoracic impedance, respiratory rate, systemic blood pressure, oxygen saturations, body weight, pulmonary artery pressure, cardiac output and stroke volume) to a hospital-based monitoring team and benefit from close contact with the specialist team while reducing travel to the hospital. Remote systemic blood pressure, oxygen saturations and body weight are provided through the FDA/CE approved Cordella Heart Failure System (24). The protocol of the FIT-PH study observational study permits evaluation of therapeutic interventions. This group of patients would be suitable for assessing the tolerability of Imatinib in Part 1 of the PIPAH study. They can provide valuable additional information on the haemodynamic response to Imatinib that cannot be obtained by other means as well as objective activity data to enable interpretation of self-reported information.

[figure not shown]

4.3.1 Inclusion criteria

- 1. Subjects aged between 18-80 years old
- **2.** PAH which is idiopathic; PAH heritable; PAH associated with connective tissue disease; PAH after ≥1 year repair of congenital systemic to pulmonary shunt; or PAH associated with anorexigens or other drugs
- 3. Subjects willing to be genotyped for genes that influence PDGF activity
- **4.** Resting mean pulmonary artery pressure ≥25 mmHg, Pulmonary capillary wedge pressure ≤15 mmHg, PVR >5 wood units, and normal or reduced cardiac output, as measured by right heart catheterisation (RHC) at entry
- **5.** Six-minute walking distance >50m at entry
- **6.** Stable on an unchanged PAH therapeutic regime comprising at least 2 therapies licensed for PAH (any combination of endothelin receptor antagonist, phosphodiesterase inhibitor or prostacyclin analogue) for at least 1 month prior to screening
- 7. Able to provide written informed consent prior to any study mandated procedures
- **8.** Contraception: Women of childbearing potential are eligible to participate after a negative highly sensitive pregnancy test if they are taking a highly effective method of contraception during treatment and until the end of relevant systemic exposure.

Fertile males who make use of condom and contraception methods during treatment and until the end of relevant systemic exposure in women of childbearing potential.

Women of childbearing potential and fertile men* are eligible to participate, if they agree to use highly effective contraceptive methods with typical-use failure rate <1% per year, when used consistently and correctly. Such methods include:

- sexual abstinence
- combined (oestrogen and progestogen containing) hormonal contraception associated with inhibition of ovulation¹:
 - o oral
 - o intravaginal
 - o transdermal
- progestogen-only hormonal contraception associated with inhibition of ovulation1:
 - o oral
 - o injectable
 - o implantable²
- intrauterine device (also called IUD)²
- intrauterine hormone-releasing system (also known as IUS)²
- bilateral tubal occlusion²
- vasectomised partner^{2,3}

For the purpose of this document, a woman is considered of childbearing potential, i.e. fertile, following menarche and until becoming post-menopausal unless permanently sterile. Permanent sterilisation methods include hysterectomy, bilateral salpingectomy and bilateral oophorectomy. A postmenopausal state is defined as no menses for 12 months without an alternative medical cause. A high follicle stimulating hormone (FSH) level in the postmenopausal range may be used to confirm a post-menopausal state in women not using hormonal contraception or hormonal replacement therapy. However, in the absence of 12 months of amenorrhea, a single FSH measurement is insufficient. For the purpose of this document, a man is considered fertile after puberty unless permanently sterile by bilateral orchidectomy.

PIPAH Study Page 23 of 47

^{*}Definition of fertile females (women of childbearing potential) and of fertile men:

¹Hormonal contraception may be susceptible to interaction with the IMP, which may reduce the efficacy of the contraception method.

²Contraception methods that in this context are considered to have low user dependency.

³Vasectomised partner is a highly effective birth control method provided that partner is the sole sexual partner of the associated female trial participant and that the vasectomised partner has received medical assessment of the surgical success.

⁴In the context of this guidance sexual abstinence is considered a highly effective method only if defined as refraining from heterosexual intercourse during the entire period of risk associated with the study treatments. The reliability of sexual abstinence needs to be evaluated in relation to the duration of the clinical trial and the preferred and usual lifestyle of the subject.

4.3.2 Exclusion criteria

- 1. Unable to provide informed consent and/or are non-fluent speakers of the English language
- 2. Hypersensitivity to Imatinib or to any of the excipients
- 3. Clinically-significant renal disease (confirmed by creatinine clearance <30 ml/min per 1.73m²)
- 4. Clinically-significant liver disease (confirmed by serum transaminases >3 times than upper normal limit)
- 5. Patients receiving oral and/or parenteral anticoagulants*
- 6. Anaemia confirmed by haemoglobin concentration <10 g/dl
- 7. History of thrombocytopenia
- 8. Individuals known to have haemoglobinopathy sickle cell disease, thalassaemia
- 9. Hospital admission related to PAH or change in PAH therapy within 3 months prior to screening
- **10.** History of left-sided heart disease and/or clinically significant cardiac disease, including but not limited to any of the following:
 - a. Aortic or mitral valve disease (stenosis or regurgitation) defined as greater than mild aortic insufficiency, mild aortic stenosis, mild mitral stenosis, moderate mitral regurgitation
 - b. Mechanical or bioprosthetic cardiac valve
 - c. Pericardial constriction/effusion with tamponade physiology, or abnormal left atrial size.
 - d. Restrictive or congestive cardiomyopathy
 - e. Left ventricular ejection fraction ≤50% (measured in echocardiogram at screening)
 - f. Symptomatic coronary disease
 - g. Significant (2+ for regurgitation) valvular disease other than tricuspid or pulmonary regurgitation
 - h. Acutely decompensated left heart failure within 1 month of screening
 - i. History of untreated obstructive sleep apnoea
- **11.** Evidence of significant lung disease on high-resolution CT (if available) or recent (performed within 12 months) lung function, where FEV1 <50% predicted and FVC <70% predicted, and DLCO (or TLCO) <50% predicted if any CT abnormalities; judged by the Site Physician
- **12.** Patients with a history of uncontrolled systemic hypertension
- **13.** Acute infection (including eye, dental, and skin infections)
- 14. Chronic inflammatory disease including HIV and Hepatitis B
- 15. Women of childbearing potential who are pregnant or breastfeeding (if applicable)
- 16. Previous intracerebral haemorrhage
- **17.** Patients who have received an IMP within 5 half-lives of the last dose or 1 month (whichever is greater) before the baseline visit
- *this does not apply to single daily antiplatelet treatment

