1.2 Imatinib

Imatinib is an orally active tyrosine kinase inhibitor (TKI) that inhibits platelet-derived growth factor receptor (PDGFR) alpha and beta, BCR-ABL, DDR and c-KIT (12). PDGF is a potent vascular smooth muscle cell mitogen (13). Studies of lung tissue from PAH patients and animal models indicate that PDGF is important in vascular smooth muscle proliferation and hyperplasia (6). Histological studies of human PAH lung show infiltration of pulmonary arterial lesions with c-kit(+) cells, which may also participate in vascular remodelling (14, 15). Imatinib consistently reverses pulmonary hypertension in experimental models (7).

These data are supported by two placebo-controlled randomised clinical trials; a Phase II involving 59 patients (9) and a Phase III including 202 patients (10) have provided evidence of clinical efficacy in PAH. The Phase III IMPRES study (10) reported a significant improvement in functional capacity (the mean placebo-corrected treatment effect on six-minute walk distance (6MWD) was 32m; 95% confidence interval, 12-52; P=0.002) and a reduction in pulmonary vascular resistance (PVR) of 379 dynes·s·cm⁻⁵ (95% confidence interval, −502 to −255; P<0.001, between-group difference) with Imatinib at 24 weeks compared to placebo in patients already receiving their licensed vasodilatory treatments (10). Unfortunately, Serious Adverse Events (SAEs) and discontinuations were more common in the Imatinib group (10).

Of particular concern, eight patients enrolled in IMPRES (10) developed a subdural haematoma while taking Imatinib, leading to death in two. These patients were taking an anticoagulant, warfarin, at the same time as Imatinib. An interaction between these two drugs is strongly suspected although the mechanism of this interaction is not known.

Despite these concerns, in the absence of alternative effective treatments, there remains considerable interest in the use of Imatinib for PAH. It is raised at all international meetings discussing PAH and drug development. As an indicator of clinical need, Imatinib continues to be used worldwide on compassionate grounds as a treatment of last resort and up to 100 patients may be taking it across Europe. Many specialist centres have case reports where patients have been 'rescued' by the drug.

Recent UK case study - April 2019

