7.9 Brain imaging

A conventional brain magnetic resonance imaging (MRI) scan will be conducted at screening (Visit 1) to exclude previous intracerebral haemorrhage. Where MRI is contra-indicated (e.g. due to metal implants and/or claustrophobia), participants will be asked to undergo a CT scan of the head at screening (Visit 1) to exclude intracerebral haemorrhage. The maximum total radiation dose from the CT scan will be approximately 2 mSv. The brain MRI scan will always be the first choice. Imaging will take place at each hospital site. All brain scans will be reported routinely. Reports will be documented on eCRFs for safety and monitoring purposes. Any incidental finding will be documented. Any abnormal finding during clinical follow-up will be considered an Adverse Event.

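### Exclusion 16 and the screening brain scan cover only intracerebral haemorrhage, although subdural haematoma is the bleed the protocol names as its concern

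*Protocol*

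**What the plan says.** Section 1.2 gives the safety background: "eight patients enrolled in IMPRES (10) developed a subdural haematoma while taking Imatinib, leading to death in two". It adds: "These patients were taking an anticoagulant, warfarin, at the same time as Imatinib". An interaction is strongly suspected, and its mechanism is said to be unknown.

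The protocol responds in two ways.

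- **Anticoagulants.** Exclusion 5 removes "Patients receiving oral and/or parenteral anticoagulants", and section 5.6.2 prohibits the same drugs during the study. A footnote to the exclusion list keeps one class of drug available: "this does not apply to single daily antiplatelet treatment".
- **Bleeding history.** Exclusion 16, in the Study Summary and in section 4.3.2, is "Previous intracerebral haemorrhage". Section 7.9 supports it with a scan of every patient. The MRI "will be conducted at screening (Visit 1) to exclude previous intracerebral haemorrhage". Where MRI is contraindicated, the patient has a "CT scan of the head at screening (Visit 1) to exclude intracerebral haemorrhage".

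Section 7.9 also says: "All brain scans will be reported routinely". Reports go on the eCRF and incidental findings are documented. Section 6.2 has the study physician review results before the first dose. Section 4.3 allows no deviation from the eligibility criteria.

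**The concern.** The rationale names one kind of intracranial bleed, and the entry rule and the scan are written for another. A subdural haematoma lies outside the brain tissue, so a haemorrhage criterion confined to the intracerebral kind does not reach it. Exclusion 16 also refers only to the past, so it does not name a bleed that is present at screening.

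Two kinds of patient are affected:

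- **A subdural collection seen on the screening scan.** It would probably be noticed before dosing, but the protocol does not say what must follow, so each of the 8 sites would decide for itself.
- **A known, resolved subdural bleed.** This may be evident only from the history, and the patient can be enrolled without breaching any criterion.

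In a trial of up to 43 patients, one serious intracranial bleed in someone whose history should have barred entry would be a safety failure. It could also put the trial at risk, given the history of this drug in this disease.

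**Working it through.** The protocol states no figure on this point, so the check is a comparison of wording.

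**Step 1: which bleed is the concern?** Section 1.2 names subdural haematoma. In the text available to this review the word appears only there. Section 1.2 names no other kind of intracranial bleed.

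**Step 2: which bleed do the safeguards name?**

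| Place | Safeguard | Bleed named |
|---|---|---|
| Study Summary, exclusion 16 | Entry criterion | Previous intracerebral |
| Section 4.3.2, exclusion 16 | Entry criterion | Previous intracerebral |
| Section 7.9, MRI sentence | Purpose of scan | Previous intracerebral |
| Section 7.9, CT sentence | Purpose of scan | Intracerebral |

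Count: 1 + 1 + 2 = 4 statements say intracerebral, and 0 of 4 say subdural or intracranial. These are one criterion printed twice and two sentences about the scan that serves it. The count shows that the wording is consistent; it does not measure harm.

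**Step 3: does another criterion catch a subdural bleed?** None of the 17 exclusions does so.

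- Exclusion 5 (anticoagulants), exclusion 7 (history of thrombocytopenia) and exclusion 12 (uncontrolled systemic hypertension) bear on bleeding risk. None is a rule about a past or present bleed.
- No exclusion leaves general unsuitability to the investigator's judgement.
- Because section 4.3 permits no deviations, the listed wording is what sites must apply.

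**Step 4: does a later provision fill the gap?**

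- The physician's review in section 6.2 carries no stated criterion for a subdural finding.
- Section 7.9 gives incidental findings no consequence for eligibility.
- The right to discontinue a subject in section 4.3.4 is a discretionary safety power, not an entry rule.
- Appendix 1 schedules brain imaging only at screening, so entry is the one planned point at which an imaging rule could act.

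**Step 5: what risk does the gap add?** This cannot be calculated. The protocol gives neither how often these patients have had a subdural bleed nor the risk of re-bleeding on imatinib without an anticoagulant. The eight cases in the earlier trial do not supply either figure: they are new bleeds in patients on warfarin.

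**The case against.** The strongest reply is that the protocol already addresses the hazard it describes. The earlier subdural bleeds arose on treatment in patients taking warfarin, an interaction is suspected, and anticoagulants are banned at entry and throughout. Nothing in the protocol says those patients had bled before, or that a past subdural bleed predicts one on imatinib. Every patient is scanned, every scan is reported, a physician reviews results before dosing, and independent committees oversee the trial. The patient who could still slip through is one with a known, resolved subdural bleed, off anticoagulants, whom a specialist chooses to enrol. That is a narrow group.

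Most of this stands, and it limits the weight of the point. The added risk from a past bleed is a clinical judgement, not something the protocol demonstrates. It does not close the gap, for three reasons.

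- The protocol keeps a haemorrhage-history exclusion and a universal brain scan on top of the anticoagulant ban, so the ban was not treated as sufficient. That second safeguard omits the bleed that was actually observed.
- The mechanism of the suspected interaction is stated to be unknown. Single antiplatelet treatment remains allowed, and section 4.1 lists unusual bleeding or bruising among the recognised effects of imatinib. These points concern bleeding in general, but they argue against treating the ban as complete cover.
- If intracranial was meant throughout, the text should say so.

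It is also fair that a blanket exclusion could bar patients with remote traumatic bleeds in a rare disease. The clinical leads should settle that in the new wording.

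**Conclusion.** The concern holds. As written, exclusion 16 and section 7.9 do not cover the type of bleed that section 1.2 identifies, and a patient with a past or current subdural haematoma can be enrolled without breaching a listed criterion. The gap is a missing decision rule, not a missing test.

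The added risk is unquantified and probably small, because the anticoagulant ban removes the suspected cause and a visible collection would probably be seen before dosing. The point should be fixed because the correction is cheap and concerns a bleed linked to two deaths.

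The conclusion rests on reading *intracerebral* in its usual sense, and on the text available. Some pages were removed from the copy reviewed, and Appendix 2 is a separate file that was not seen.

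**What to change.** Replace the wording in four places: exclusion 16 in the Study Summary, exclusion 16 in section 4.3.2, and the MRI and CT sentences of section 7.9. Each should refer to *previous or current intracranial haemorrhage, including subdural haematoma*. The clinical leads should decide whether to qualify this, for example for remote, fully resolved traumatic bleeds, and write any qualification into the criterion so that all sites apply the same rule.

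The cost is four phrases in three sections. Because an eligibility criterion changes, section 11.5 requires a formal amendment submitted to the authorities and the ethics committee for approval before it takes effect, so it is best combined with the next planned amendment. No test is added, since every patient already has the scan, and the sample size and analysis do not change. The downside is very few extra screen failures.

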4.3.3 Subject completion

Subjects will be considered complete for the purpose of this study once they have completed all procedures of the follow-up telephone assessment or unscheduled visit at the end of Week 28 (or 4 Weeks after early termination). The end of the clinical trial is defined as the last assessment of the last subject undergoing the trial.

4.3.4 Discontinuation criteria

It is possible that the Sponsor or the Competent Authorities request termination of the study if there are concerns about conduct or safety, or due to a change in the opinion of the Ethics Committee.

When the Sponsor is aware of information on matters concerning the quality, efficacy, and safety of the study drug, as well as other important information that may affect proper conduct of the clinical study, the Sponsor may discontinue the clinical study and send a written notice of the discontinuation along with the reasons to the Investigators. Patients will be informed that they have the right to withdraw from the study at any time for any reason, without prejudice to their medical care. The site Investigator/Chief Investigator can discontinue subjects from the study for any of the following reasons:

- 1. Occurrence of an unacceptable Adverse Event due to Grade 2 or above defined by the NCI Common Terminology Criteria for Adverse Events (version 5.0, 2017), adapted for this study -see Appendix 2.
- 2. Subject request
- 3. Subject is lost to follow-up
- 4. Administrative reasons
- **5.** Development of an intercurrent illness, condition, or procedural complication, which would interfere with the subject's continued participation
- 6. Patient becomes pregnant

The site Investigator/Chief Investigator also reserves the right to discontinue subjects in the interest of subject safety and welfare. Investigators must contact all participants and the hospital pharmacy (where applicable) to notify them of the termination of the study. In cases of an early termination (discontinuation), a follow-up telephone assessment will be performed 4 weeks ± 3 days -see Appendix 1.

4.3.5 Subject identification and replacement policy

After informed consent is obtained, patients who are screened will be assigned a 7-digit permanent identification number (subject ID) such that all patients from each research site are given consecutive identification numbers in successive order of inclusion. The first 4 digits of the will be the designated research site ID, and the last 3 digits will be assigned at the research study centre (e.g., if the site ID is 4410, the third patient screened at 4410 site, would be given the number of 4410003).

A patient who is screened but fails to proceed into baseline assessment (e.g., because entry criteria were not met or enrolment did not occur within the specified time frame) may be considered for screening again. Rescreening will be permitted by the site Investigator on a case-by-case basis. A new informed consent form will be signed in any case of re-screening. A new subject ID will be assigned to the subject. Patients who are discontinued will be replaced. Each replacement is by a default a new subject, who will be assigned a completely new subject ID.

